### 4.1 Study Phases

There will be three phases of the overall HOPE-2 study identified in the analysis, defined as follows:

- 1. **Main Phase**: The double-blind HOPE-2 study which followed subjects from baseline through 12 months of follow-up. Twenty subjects completed this study. Of these 20 subjects, 13 enrolled in the HOPE-2-OLE study.
- 2. **Gap Phase:** The gap period, approximately 1 year for each of the 13 subjects, between the end of HOPE-2 12-month visit and the Baseline visit of the OLE Phase.
- **3. OLE Phase:** The unblinded open-label extension study (HOPE-2-OLE) described in this SAP and cited protocol, consisting of 13 subjects all treated with deramiocel for up to 57-months.

# 4.2 Treatment Groups

The treatment group to be presented will be composed of all subjects enrolled in this open label study. All subject in this study were assigned to receive deramiocel. The original treatment group (HOPE-2 Phase 2 study) for each of these subjects also will be considered. In addition, External Comparator (EC) data will be utilized to further examine the PUL 2.0 Combined Total Score and selected cardiac MRI parameters, labeled as ECP and ECC, respectively.

# 4.3 Study Day

The day of first IP administration is defined as Day 1. All other study days will be labeled relative to Day 1. Thus, study day for a particular event date on or after Day 1 is calculated as: (*Date of event – Date of first IP administration + 1*). An event that occurs prior to Day 1 is calculated as: (*Date of event – Date of first IP administration + 1*).

The duration of an event will be calculated as *(Event end date – Event start date + 1)*. Day 0 will not be used.

The baseline value for each subject is the last non-missing value that is obtained prior to the time of the first IP administration on Day 1.

# 4.4 Handling of Dropouts or Missing Data

Subject-level listings will present data as reported. Missing or partially missing dates that are required for date-dependent definitions (e.g., TEAEs, concomitant medications) will be assumed to be the most conservative date possible.

An adverse event (AE) with a completely missing start date will be considered treatmentemergent; similarly, an AE that started the same month and year as IP administration, but with a missing start day, will be considered treatment-emergent.

When the PUL 2.0 Combined Total Score [high-level (shoulder) + mid-level (elbow) + distal level (wrist and hand] is calculated, there are subjects who cannot do the High-Level Shoulder regional assessment due to incapacity. In cases where sites left this subcategory blank rather than entering a 0, a 0 will be entered for analysis to permit calculation of the total. It should be noted that a higher score indicates higher functioning thus allowing a 0 for calculation purposes still reflects the overall incapacity of the subject.

Modest imputation of missing data is planned when modelling; this is to linearly impute missing item scores from the PUL 2.0, when those item scores are observed before and after the missing visit.

Medical history with missing stop dates will be considered ongoing. Medications with missing stop dates will be considered as concurrent use during the study and will be counted in the summary table of concomitant medications unless the start date is after the last IP administration.

Data from any subject who early terminates (ET) will be treated as follows:

• Map ET data to a scheduled visit according to the protocol defined windows (See Appendix A Section 9.1)

• If the ET data does not fall in any visit window, the ET data will be considered to have been collected at an unscheduled visit and excluded from analysis and summary tables.

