## 12.1. Performance of Upper Limb

The Performance of Upper Limb (PUL) was designed specifically for assessing upper limb function in ambulant and non-ambulant DMD patients (Pane et al., 2014). All the tasks included in the PUL were selected to address patient prioritized activities of daily living that are typical regardless of age, including preschool children. The PUL includes an entry item to define the starting functional testing level for a subject. The remaining PUL items are divided into three regional dimensions: high-level (shoulder), mid-level (elbow), and distal-level (wrist and hand). Trial subjects will complete testing for PUL 2.0 in the same preferred arm throughout the course of the trial.

Elbow contractures will be measured in each arm of a subject prior to the start of PUL 2.0 testing at each visit that requires testing.

PUL equipment will be standardized across investigative sites and provided by Capricor. Every effort should be made to complete a subject's PUL 2.0 assessment at approximately the same time in the morning at each required visit. In addition, each subject should be assigned a single evaluator for testing. Additional details regarding the PUL 2.0 requirements can be found in the trial's Manual of Operations and Clinical Evaluator Binder.

Patients will undergo PUL 2.0 assessment at Day 1, Months 3, 6, 9, 12 ( $\pm$ 14 days, each), 15, 18, 21, 24, 27, 30, 33, 36, 39, 42, 45, 48, 51, 54, 57, and 60 ( $\pm$ 21 days, each). All attempts will be made to perform PUL 2.0 assessment at the specified visits. In the event a subject cannot complete the entire PUL 2.0 assessment, it should be marked as not done. For example, if a patient has a broken arm, the entire PUL 2.0 assessment should not be completed until such time that the broken arm resolves.

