#### 13.5.2. Missing Data

There are no plans for imputation of missing data, except to linearly impute missing item scores from the PUL 2.0, when those item scores are observed before and after the missing visit, and at least 50% of the other items in the PUL 2.0 total score are non-missing. The reasons for missing data will be documented. Sensitivity analyses, however, may be performed using various assumptions for missing data to assess the impact on summary results.

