# **8 DEVIATIONS FROM STATISTICAL METHODS IN THE PROTOCOL**

The statistical methods in this statistical analysis plan are consistent with those described in the Amendment 5 of the study protocol with the following exceptions:

- The wall thickness percentages for the cardiac MRI parameters (secondary efficacy) were not collected and thus not available for descriptive analysis.
- Cardiac MRI parameters were not collected at 12-months for the HOPE-2-OLE study.
- The secondary analyses (Distal level PUL 2.0 and Mid-level (elbow) PUL 2.0) which involved subgroup analyses based on the entry level item of PUL 2.0 at baseline will be reported without the subgroups due to the small sample size of the subgroups.

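### SAP 4.4 omits the protocol's 50%-of-items condition for interpolating PUL 2.0 scores, and SAP Section 8 does not list the change (minor)

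*SAP*

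**What the plan says.** Protocol 13.5.2 starts from no imputation and makes one exception: "There are no plans for imputation of missing data, except to linearly impute missing item scores from the PUL 2.0". The exception has two conditions. The item must have been scored on both sides of the gap, and "at least 50% of the other items in the PUL 2.0 total score are non-missing". The section then leaves room for other approaches: "Sensitivity analyses, however, may be performed using various assumptions for missing data to assess the impact on summary results".

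SAP 4.4 states its rule as "this is to linearly impute missing item scores from the PUL 2.0, when those item scores are observed before and after the missing visit". This is the protocol's first condition without the second. The SAP also confines the imputation to modelling, a limit that the protocol does not set. No other part of the SAP brings the 50% condition back.

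SAP Section 8 says that the SAP's methods "are consistent with those described in the Amendment 5 of the study protocol with the following exceptions". It lists three exceptions: the wall thickness percentages, the absence of cardiac MRI at Month 12, and the dropped entry-level PUL subgroups. The imputation rule is not among them.

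Protocol 12.1 bears on what kind of missing data will arise: "In the event a subject cannot complete the entire PUL 2.0 assessment, it should be marked as not done".

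**The concern.** The two documents give different rules for the same data, and Section 8 implies that they agree. The dropped clause is the part of the rule that keeps a wholly missed visit missing. Without it, an analyst following the SAP to the letter could build a complete PUL 2.0 record for a visit at which nothing was measured. The flanking scores need not come from adjacent visits, so a run of missed visits could be filled as well.

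A random-slope mixed model already uses subjects with gaps in their follow-up. Interpolated points lie between their neighbours by construction, so they carry no new information, yet the model counts them as observations. What is at stake is the residual variance and, through it, the precision claimed for the ECP slope comparison. The accuracy of Section 8 as a record of departures from the protocol is also at stake.

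**Working it through.** **1. The two rules side by side.**

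| | Protocol 13.5.2 | SAP 4.4 |
|---|---|---|
| Item scored before and after the gap | required | required |
| At least 50% of the other items present | required | not mentioned |
| Scope | not limited | modelling only |
| Listed in SAP Section 8 | – | no |

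**2. Which visits are treated differently.** Let the scale have K items, of which m are missing at a visit with complete visits on both sides. For a missing item, the share of other items present is (K − m)/(K − 1). The protocol imputes if this is at least 0.5. The SAP imputes for any m up to K. The K values below are assumed.

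- K = 10: m = 5 gives 5/9 = 0.56 (impute); m = 6 gives 4/9 = 0.44 (do not).
- K = 20: m = 10 gives 10/19 = 0.53 (impute); m = 11 gives 9/19 = 0.47 (do not).
- K = 30: m = 15 gives 15/29 = 0.52 (impute); m = 16 gives 14/29 = 0.48 (do not).
- Any K with m = K (visit wholly missed): 0/(K − 1) = 0. The protocol never imputes; the SAP wording does.

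Protocol 12.1 turns an incomplete assessment into one marked as not done, so m = K is the usual pattern. A final visit, or follow-up lost after dropout, has no later score and cannot be interpolated under either rule.

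**3. Where the filled visits would enter.** The SAP's PUL 2.0 model is the ECP comparison in SAP 6.4: a random-slope mixed model reporting a slope difference and a treatment difference at 36 months, with confidence interval and p-value. The primary Month 12 analysis in SAP 6.2 is descriptive.

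**4. Size.** The documents give no missed-visit rate, variance or comparator number, so these are all assumptions. Visits are quarterly from Month 0 to Month 36.

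*Within-subject effect.* Least-squares slope per subject, unit residual variance, 20,000 replicates, the 11 interior visits missed at random:

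| Missed rate | Filled visits per subject | Residual variance, unfilled | Residual variance, filled | Estimated/true slope variance, unfilled | Estimated/true slope variance, filled |
|---|---|---|---|---|---|
| 10% | 1.1 | 0.99 | 0.93 | 1.01 | 0.85 |
| 20% | 2.2 | 1.00 | 0.86 | 1.01 | 0.72 |
| 30% | 3.3 | 1.00 | 0.79 | 1.00 | 0.59 |

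*Random-slope REML fit.* 13 treated (from the SAP) against 40 comparators (assumed), slope SD 1.0 per year, residual SD 1.2, 120 replicates:

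- 15% missed: residual variance 1.446 unfilled, 1.310 filled; 1 − 1.310/1.446 = 9%.
- 30% missed: 1.457 unfilled, 1.173 filled; 1 − 1.173/1.457 = 19%.
- The slope standard error moved by 2 to 5%.

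A further REML simulation with the same group sizes and missed rates gave residual variance 11 to 22% too low. Slope standard errors with and without filling were 0.333 and 0.334 in one case and 0.339 and 0.340 in the other, a difference of 0.001/0.333 = 0.3%.

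*Why the standard error barely moves.* Under the variances assumed above and complete visits, the sum of squared time deviations is 0.25² × 13 × (13² − 1)/12 = 11.375 years². The within-subject part of a slope's variance is 1.44/11.375 = 0.127, against a between-subject part of 1.0. The standard error of the slope difference is √[1.127 × (1/13 + 1/40)] = 0.339. The within-subject part is 0.127/1.127 = 11% of the total. Cutting it by 22% lowers the total by about 2.5% and the standard error by about 1.2%.

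**The case against.** The strongest case on the other side is that this is a clause lost in an almost verbatim copy. The SAP speaks of modest imputation of item scores and never says that whole visits will be filled. Protocol 13.6 leaves additional efficacy analyses to the SAP. The one affected model is exploratory, carries no multiplicity-controlled claim, and under SAP 6.4 will not be run if the matched cells are too small. Most of this stands, and it is why the point is minor. It does not remove the mismatch: the SAP's wording permits whole-visit filling, nothing labels the rule a sensitivity analysis, and Section 8 omits it.

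A reader might infer several stronger points that the documents do not support.

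- *That the primary summary would change, for example from n = 13 to n = 12.* This needs a partly missing Month 12 assessment that meets both protocol conditions, and Protocol 12.1 should make that rare. A Month 12 assessment marked as not done stays missing in the primary summary under both documents. The partial pattern that the SAP does foresee, a blank shoulder section, has its own zero-fill rule.
- *That the protocol forbids whole-visit filling.* It plans no imputation beyond its exception, but it allows other assumptions in sensitivity analyses.
- *That the results could not be reproduced.* Linear interpolation is deterministic, and filling interior visits adds records, not subjects. The defect is disagreement between the documents.
- *That the ECP inference would be materially distorted.* The residual variance is understated, but the slope standard error, which drives the reported interval and p-value, changes little.

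**Conclusion.** The point holds as a discrepancy between the documents with a limited statistical consequence. SAP 4.4 drops a condition that Protocol 13.5.2 sets, and the Section 8 statement of consistency is inaccurate on this item. Taken literally, the SAP admits interpolated whole visits into the exploratory ECP model of PUL 2.0.

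With 15 to 30% of visits missed, 13 treated subjects and 40 comparators, the residual variance would be about 10 to 20% too low and the slope standard error would change by 0 to 5%. Those figures rest on assumed rates, variances and comparator numbers. A between-subject slope variance smaller than assumed would leave less dilution and a larger effect on the standard error; fewer missed visits would make the effect smaller. The text comparison and the result for a wholly missed visit need none of these assumptions. Severity: minor.

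**What to change.** Add the protocol's 50% condition to the imputation sentence in SAP 4.4. Wholly missed visits then stay missing, and the mixed model is fitted only to observed or partly imputed visits. If the sponsor intends a different rule, it should be listed and justified in Section 8, and the ECP model should also be reported without interpolated visits.

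There is no need to prescribe the item-level rule for the comparator data. The documents do not show that serial item scores exist there, and SAP 6.4 allows for summary-level data.

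The cost is one clause in the SAP, and a few wholly missed visits remain missing. The mixed model handles such gaps without filling.

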#### 2.2.4 Secondary Efficacy Endpoints

The *secondary efficacy endpoints* include the change from baseline (PUL 2.0: HOPE-2-OLE Baseline, Cardiac MRI: HOPE-2 Screening Baseline) through Month 60 for the following:

- Upper body functionality using the PUL 2.0 assessment (i.e. Upper level PUL:2.0) at Months 24, 36, 48, and 60
- Distal level PUL 2.0 for subgroup of subjects with entry level PUL 2.0 scores of 2 and 3, at Month 12, 24, 36, 48, and 60
  - Entry level at baseline of HOPE-2-OLE
- Mid-level PUL 2.0 for subgroup of subjects with entry level PUL 2.0 scores of 4 and 5, at Month 12, 24, 36, 48, and 60
  - Entry level at baseline of HOPE-2-OLE
- Left Ventricular Ejection Fraction (LVEF (i.e. Cardiac MRI) at Month 24, 36, 48, and 60.
- Left Ventricular End Systolic Volume, Indexed (Cardiac MRI) at Month 24, 36, 48, and 60.
- Left Ventricular End Diastolic Volume, Indexed (Cardiac MRI) at Month 24, 36, 48, and 60
- Other cardiac parameters, including but not limited to mass, unindexed volumes, and end diastolic and end systolic wall thickness at 24, 36, 48, and 60

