The treated and matched controls from the ECP/ECC will be compared using a continuous-time, random slope mixed model with age, baseline, and treatment-by-time interaction. If significant baseline imbalances persist after cohort matching, a baseline-by-treatment interaction term will be included in the model. Slope differences between groups will be presented along with the estimated treatment difference at 24 months (for ECC) and 36 months (for ECP) with corresponding 95% confidence intervals and associated two-sided p-values. The Kenward Roger approximation will be utilized to calculate denominator degrees of freedom. A percentile rank transformation will be applied to the change from baseline and baseline values in case model assumptions are violated.

Furthermore, a global statistical test (GST) may be employed to explore the totality of evidence across multiple cardiac endpoints, such as Left Ventricular Ejection Fraction, Indexed Left Ventricular End Systolic Volume, Indexed Left Ventricular End Diastolic Volume, and other cardiac MRI measures collected in HOPE-2 OLE and in the ECC. The GST will be constructed as follows:

• For each distinct parameter in the GST, calculate the standardized change from baseline as follows:

$$chg'_{i,t,p} = \frac{x_{i,t,p} - \mu_p}{\sigma^{pooled}_{t,p}}$$

where *i*, *t*, *p* represent the *i*th subject, the timepoint (visit) *t*, and the *p*th parameter in the GST, *x* represents the raw score (analysis value),  $\mu$  represents the mean baseline value for parameter,  $\sigma^{pooled}$  is the standard deviation of  $x_{t,p}$  pooled between control and treatment arms, and *chg'* is the standardized change from baseline.

Then, by subject and visit, calculate the mean standardized change from baseline as:

$$chg_{i,t}^{gst} = \frac{1}{n} \sum_{p=1}^{n} chg_{i,t,p}',$$

where  $chg^{gst}$  represents the change from baseline score of the GST.

Baseline values will be calculated in the same manner using baseline analysis values for each parameter and only with the baseline visit. If any of the baseline components do not have a calculable baseline value, baseline will be calculated from the available measures. Scales will be directionally aligned in determination of the final score.

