### 6.5 Sensitivity Analyses

Sensitivity analyses will be performed to test the robustness of the External Comparator analysis results for LVEF. Analyses exploring the hyperparameters of the propensity score matching algorithm will be presented. Random ordering will be employed to test the sensitivity of the match algorithm to sort order. Furthermore, results from an optimal propensity matching algorithm with appropriate k and caliper width will be presented.

The following outcome analyses will be performed using the matched set from the primary analysis:

- A Wilcoxon rank test comparing the change from baseline between the two groups,
- Change from baseline to Month 24 using an ANCOVA model with treatment as a factor and baseline and age as potential covariates.

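### SAP 4.4 drops out-of-window early-termination values with no exception for the SAP 6.4 slope models; separately, the cardiac model's 24 months has no stated origin

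*SAP*

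**What the plan says.** **ET data.** SAP 4.4 has two steps for a subject who leaves early. Data dated inside a visit window are mapped to that visit. If no window contains the date, "the ET data will be considered to have been collected at an unscheduled visit and excluded from analysis and summary tables". The windows are 14 days either side at Months 3 to 12 and 21 days either side at Months 15 to 60. SAP 4.4, 6.4 and 6.5 state no exception for models. Listings still show the data as reported.

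**The models.** SAP 6.4 compares OLE subjects with external controls on PUL 2.0 (ECP) and cardiac MRI (ECC). It uses a "continuous-time, random slope mixed model" with a treatment-by-time interaction. It reports the slope difference and an estimated difference at 24 months for ECC and 36 months for ECP.

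**By-visit analyses.** The instruction for the global statistical test (GST) reads "by subject and visit, calculate the mean standardized change from baseline". The LVEF sensitivity analyses in SAP 6.5 include a Wilcoxon test and "Change from baseline to Month 24 using an ANCOVA model with treatment as a factor".

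**What is collected at withdrawal.** Protocol 7.4 asks that the Month 60 assessments be attempted, and the schedule of assessments includes PUL 2.0 among them. Protocol 12.2 lists cardiac MRI at the Early Termination Visit.

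**Dates.** SAP 4.3 makes the first infusion Day 1: "All other study days will be labeled relative to Day 1". SAP 6.3 and 6.4 take HOPE-2 Month 12 as the cardiac MRI baseline. SAP 4.1 puts the Gap Phase between that visit and the OLE baseline at "approximately 1 year for each of the 13 subjects". SAP 2.2.4 has "Cardiac MRI: HOPE-2 Screening Baseline".

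**The concern.** A rule that discards values lying between windows suits tables laid out by visit. It does not suit a model in continuous time, which can take each value at the date it was measured. The values at issue are ones the protocol makes a special effort to obtain, and they are the last observations before a subject leaves.

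A mixed model copes with dropout to the extent that the data it is given explain the dropout. Removing the last value before withdrawal removes the part most likely to do so. If subjects withdraw because they are declining, the fitted slope for treated subjects could look better than it should. With 13 treated subjects there is little other data to compensate.

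A second question would exist even if nobody left early. The ECC model reports a difference at 24 months, and the SAP gives more than one candidate for the date from which those months run.

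**Working it through.** The plan gives no figure to reproduce here: no dropout rate, no ET dates and no power calculation. The check is mainly of text, with a little arithmetic.

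**1. Does the exclusion reach the slope models?** SAP 4.4 names analysis as well as summary tables. Where the SAP means that unscheduled data are listed and nothing more, it can say so, as SAP 7.2 does for vital signs. The plain reading therefore covers SAP 6.4. A tables-only reading is possible, and the text does not exclude it.

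**2. Do those models need windows?** Not if time is elapsed time, which is the natural meaning of continuous time, although SAP 6.4 does not define the variable. Protocol 12.2 also lets the Month 24 MRI run late and moves later MRIs with it, so scheduled MRIs can already depart from nominal months. The GST, the Wilcoxon test and the Month 24 ANCOVA do need a visit label, and the exclusion is reasonable for them.

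**3. What would one affected subject lose?** This applies only to a subject who has an out-of-window ET value.

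- PUL 2.0: with k scheduled post-baseline visits attended and one ET value, the share lost is 1/(k + 1). If the last visit is Month 3, k = 1 and the loss is 1/2. If it is Month 33, k = 11 and the loss is 1/12.
- Cardiac MRI: the first scheduled OLE scan is at Month 24. A subject who leaves before that window has no scheduled post-baseline MRI, so excluding the ET scan takes the count from 1 to 0. The schedules mark earlier MRI as standard of care, so other scans may exist; the SAP does not say whether the model would use them.

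**4. Where do the ECC model's 24 months start?** Let g be the gap in months between HOPE-2 Month 12 and OLE Day 1. SAP 4.1 supports g of about 12; I assume 6 to 18 as a range.

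| Origin | Months after the HOPE-2 Month 12 MRI | Position in the OLE |
|---|---|---|
| HOPE-2 Month 12 (SAP 6.3, 6.4) | 24 | Month 24 − g = 12 (range 18 to 6) |
| OLE Day 1 (SAP 4.3) | 24 + g = 36 (range 30 to 42) | Month 24 |

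The ratio of the two intervals is 36/24 = 1.5 (range 1.25 to 1.75). On the first reading the estimate falls near OLE Month 12, where SAP 8 records that no MRI was collected. On the second it falls at the first scheduled OLE MRI, and the change from baseline spans the Gap Phase. SAP 6.3 and 6.5 refer to Month 24 as a visit, which leans towards the second reading, but SAP 6.4 does not adopt it. SAP 2.2.4 names a third date, the HOPE-2 screening baseline, for change from baseline in cardiac MRI.

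**5. Does the same doubt apply to PUL 2.0?** Not for treated subjects. SAP 6.2 and 6.3 use the OLE baseline (Day 1 in SAP 6.2), and SAP 4.3 counts from Day 1. For comparator subjects, SAP 6.4 gives no index date in either model.

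**The case against.** **The rule is objective and the stakes are modest.** It is set in advance and needs no judgement about outcomes. The models are exploratory, there are no formal hypotheses, and SAP 6.4 allows the comparator analyses not to be run if numbers are too small after matching. All of this stands, and it limits the weight of the point. It does not explain why a continuous-time model should discard dated values.

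**A reader might infer a data-loss rate from the windows.** Take a month as 30.44 days and count nominal days 1 to 1826. The windows cover 4 × 29 + 15 × 43 + 22 = 783 days, leaving 1043 (57%) outside. That is a share of calendar days, not of subjects or values. Nothing suggests that ET visits fall evenly over days, and infusions are anchored to the previous infusion (Protocol 8.3), so the windows are only nominal. The one timing the protocol gives, at least 3 months after the last infusion for safety withdrawals (Protocol 7.4), has its minimum on the next target date, inside a window. The 57% should not be used as the magnitude.

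**A reader might infer that a treated subject, 1 of 13 or about 8%, drops out of the ECC model.** That needs several things together: withdrawal before the Month 24 window, a completed ET MRI, a date outside every window, the broad reading of SAP 4.4, no other usable scan, and a model that is actually run. The documents establish none of these events.

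**A reader might say that time zero is undefined throughout.** That goes too far. For PUL 2.0 the treated subjects' dates agree. For cardiac MRI, SAP 6.4 does name a baseline visit. What is missing is a statement that this visit is the model's time origin, and an index date for comparator subjects. This question is also independent of the ET rule and adds nothing to the case against it.

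**Conclusion.** The point holds as a low-cost correction worth considering. On its plain wording, SAP 4.4 keeps out-of-window ET values of PUL 2.0 and cardiac MRI out of slope models that could use them. This rests on reading the exclusion as covering models and the model's time as elapsed time; both are the natural readings, and neither is stated.

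The size cannot be given, because the documents contain no ET dates or dropout rate and the number affected may be zero. Bias is a possibility that depends on withdrawal being related to decline, which is not shown. By-visit tables, listings and the Month 12 primary summary are unaffected.

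The separate cardiac finding does not depend on any dropout. As written, the ECC estimate is 24 months or about 36 months after the HOPE-2 Month 12 MRI (30 to 42 on the second reading for the assumed gaps), and SAP 6.4 does not say which. If treated subjects were counted from OLE Day 1 and controls from their own baseline scan, changes over unequal intervals would be compared.

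**What to change.** 1. In SAP 4.4, keep the exclusion for by-visit tables and by-visit analyses (GST, Wilcoxon, Month 24 ANCOVA). State that it does not apply to the SAP 6.4 slope models, where ET PUL 2.0 and MRI values enter at their actual assessment dates.
2. In SAP 6.4, define time as elapsed time from the baseline assessment, in the same way for treated and comparator subjects, and give the comparators' index date.
3. Reconcile the cardiac baseline across SAP 2.2.4, 6.3 and 6.4, and state the date from which the 24-month ECC estimate is counted. If it is the HOPE-2 Month 12 MRI, acknowledge that the estimate falls near OLE Month 12, where no MRI was collected.
4. Report how many ET values lay outside every window, and run each comparator model once without them as a sensitivity analysis.

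The cost is one sentence in SAP 4.4, a few in SAP 6.4, a consistent baseline entry in SAP 2.2.4, and one extra model run per comparator. No new data are needed, and the by-visit results do not change because of the ET provision.
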